16.2.4.1.3. LME Model for Annual Rate of Change

The annual disease progression between each mITT population and all controls will be compared using an LME model for each key secondary efficacy variable. The same model described in [Section 16.2.3.3](#) will be used. Separate analyses of baseline asymptomatic and symptomatic subjects will also be made to determine if treatment before symptom onset is different from after symptom onset.

The same analysis will also be conducted for the six subgroups defined in the first paragraph in [Section 16.2.4.1.1](#).

16.2.4.1.4. Exponential Disease Progression Model

The exponential disease progression model with EYO as the continuous time variable as presented below will be applied to CDR-SB. The model will be used to estimate the slowing of disease progression in the OLE Gant mITT population compared to all controls. Because the baseline values of the OLE Gant mITT population were obtained before the treatment, these values will be counted into all controls for estimating the disease progression over EYO.

Briefly, the model can be described as:

$$Y_{ijk} = (\beta + \mu_i) + \gamma_{1k} * e^{\left(\frac{EYO_{ij} + \delta_i}{\gamma_{2k}}\right)} + \varepsilon_{ijk}$$

Where, y_{ijk} denotes the assessment for subject i at visit EYO j in treatment arm $k = 1, 2$; treatment is a categorical variable with two categories: subjects the OLE Gant mITT population (only post OLE baseline data), and subjects in all controls (data in this category include: baseline data of the OLE Gant mITT population and data of all controls); β is the mean of the healthy period (e.g. EYO ≤ -15) and is assumed to be the same for all arms; γ_{1k} is the mean decline

Author: [REDACTED]

Version Number:

7

Version Date:

07Dec2023

Template No.: CS TP BS016 Revision 6

Reference: CS WI BS005

Effective Date: 02Dec2019

from the healthy period to symptom onset (e.g. EYO=0); I is the indicator function with $I(k = 2) = 1$; μ_i and δ_i are the subject-level random effects and are assumed to follow a bivariate normal distribution; ε_{ijk} is the within- subject error and is assumed to follow a normal distribution $N(0, \sigma^2)$; and γ_{2k} represents the scale parameter of the treatment and all control group.

The null hypothesis is: $\gamma_{21} = \gamma_{22}$;

and the alternative is: $\gamma_{21} \neq \gamma_{22}$:

The same analysis will also be applied to the OLE Gant mITT population and the OLE Gant All Gant exposure mITT populations, along with all controls. The analysis will also be conducted for each population based on the baseline asymptomatic and symptomatic subjects presented separately.

The spaghetti plots of individual will be presented over time since baseline and over EYO for both the OLE Gant mITT population and all controls.

Figures of model estimated mean over EYO by treatment arms or spaghetti plots of individual data over EYO by treatment arms will be presented as deemed necessary by Washington University team and may be included in CSR as needed.

The same analysis will also be conducted for the six subgroups defined in the first paragraph in [Section 16.2.4.1.1](#).

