3 STUDY PROCEDURES

3.1 Enrollment

Refer to prior protocol amendments for details associated with randomization into the double-blind period; see details in Section 3.4 of the main protocol.

After completion of the double-blind period, both the gantenerumab and solanezumab arms were analyzed and it was determined that the gantenerumab OLE period would proceed with enrollment. Any participant from either the gantenerumab or solanezumab blinded drug arms is eligible to enroll in the OLE period once confirmed as a mutation carrier, and having met the continuing eligibility requirements outlined in OLE V1 procedures (Section 3.2.1). Eligible participants were able to start treatment in the OLE period after the final analysis of the double-blind treatment period had been completed.

Figure 2 Enrollment Diagram: DIAN-TU-001 Gantenerumab Open Label Extension Period

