The double-blind period had two arms for each study drug, the active study drug and the blinded placebo for that study drug. Subjects were recruited from various sources, i.e., participating DIAN-observational (DIAN-OBS) study sites, DIAN-TU-001 trial sites, DIAN-TU-001 partner sites, the DIAN Expanded Registry study, and families identified by the sites. Mutation positive subjects who signed the informed consent form (ICF), met eligibility requirements and completed all baseline evaluations were randomized in a 3:1 ratio to receive either the active study drug or placebo for the active study drug. Eligible subjects were offered the opportunity to receive active drug for up to 3 years in an open label extension.

Mutation positive subjects who were administered either gantenerumab/placebo to gantenerumab or solanezumab/placebo to solanezumab were allowed to participate in the OLE for gantenerumab. All subjects participating in the OLE will receive gantenerumab. Dosing and titration for the OLE can be found in Section 1.5.2 of Appendix 3 of the protocol.

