5.3. MODIFIED INTENT-TO-TREAT [mITT]

The mITT analysis populations include all enrolled mutation positive subjects who receive any treatment post-baseline and have at least one assessment for the analysis primary parameter (PiB-PET SUVR for final analysis, CDR Global for both the interim analysis and the final analysis) prior to the associated treatment period (as a baseline assessment) and a post-baseline assessment. For analysis of clinical/cognitive endpoints or non-PET biomarker endpoints, the mITT population identified based on CDR Global should be used.

Author: [REDACTED]

Version Number:

7

Version Date:

07Dec2023

[figure not shown]
Template No.: CS_TP_BS016 Revision 6

Reference: CS_WI_BS005

Effective Date: 02Dec2019

There will be three separate mITT populations:

1. OLE Gant mITT: Any subjects in the OLE meeting mITT criteria using OLE baseline (defined as the last assessment time for the analysis primary parameter prior to the first dose of OLE treatment) as the baseline reference point. Refer to figure below where the data contributing to the population is highlighted in yellow (and denoted with '(Tx)') for the OLE period, regardless of double-blind treatment, with controls (further described in [Section 5.4](#)) highlighted in green from both placebo double-blind only subjects and matched controls from DIAN-OBS.

2. OLE Gant All Gant exposure mITT: Any subjects treated with gantenerumab in both the DB and OLE who meet mITT criteria using DB baseline as the baseline reference point. Refer to figure below where the data contributing to the population is highlighted in yellow (and denoted with '(Tx)') for subjects treated with gantenerumab in both DB and

Author: [REDACTED]

Version Number:

7

Version Date:

[figure not shown]
07Dec2023

Template No.: CS_TP_BS016 Revision 6

Reference: CS_WI_BS005

Effective Date: 02Dec2019

OLE, with main set controls (further described in [Section 5.4](#)) highlighted in green from both placebo double-blind only subjects and matched controls from DIAN-OBS, and an additional set of extended controls (using DB and OLE baseline values for double-blind placebo subjects entering OLE) in a different shade of green to be added to the main set controls to form a second set of controls for the population.

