5.4.2. INTERNAL SET CONTROLS

The internal set controls are defined as the placebo data from the double-blind period among subjects who did not enter the open-label extension.

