6.2.2. OLE BASELINE

OLE Baseline is defined as the latest non-missing DIAN-TU-001 measurement taken prior to OLE study drug administration, using data from the OLE database where applicable. OLE baseline for specific assessments are as follows:

- OLE baseline for CDR Global and CDR-SB will be defined as the latest non-missing measurement prior to OLE study drug administration.
- For blood pressure, OLE baseline will further be defined as the latest time prior to OLE study drug administration where both systolic and diastolic blood pressure measurements are available.
- For laboratory assessments, OLE baseline will be defined as the values at Visit 1 of the OLE.
- OLE baseline measurements for height and weight will be derived from the values at Visit 1.

OLE Baseline will not be defined for subjects who never took the study drug. For assessments collected without a time measurement on the date of the first dose, the assessment can contribute

Author: [REDACTED]

Version Number:

7

Version Date:

07Dec2023

Template No.: CS_TP_BS016 Revision 6

Reference: CS_WI_BS005

Effective Date: 02Dec2019

to OLE baseline if it was scheduled per protocol to take place prior to dosing.

Baseline for DIAN-OBS will be defined based on the first visit in which the subject met criteria as described in [Section 5.4](#), noting that this visit will be identified at the time the subject is identified to contribute to the external controls.

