16.2.4.1.2. Cox Proportional Hazards Model for Time to First Disease Progression in CDR SB

The analysis models in **Section 16.2.3.2** (Cox proportional hazards model) will be applied to CDR SB. The same analysis will be repeated for the OLE Gant mITT population with 4 treatment groups (subjects on gantenerumab in the double-blind period, subjects on solanezumab in the double-blind period, subjects on placebo in the double-blind period, and all control) and will be repeated for the six subgroups defined in the first paragraph in **Section 16.2.4.1.1**. The same analysis may also be conducted for subgroups defined in the second paragraph in **Section 16.2.4.1.1**.

[REDACTED] [REDACTED]

Author: [REDACTED]

Version Number:

7

Version Date:

07Dec2023

Template No.: CS_TP_BS016 Revision 6

Reference: CS_WI_BS005

Effective Date: 02Dec2019

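### Two supplemental progression models count OLE baselines taken after double-blind gantenerumab as control data

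*SAP*

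**What the plan says.** SAP 16.2.4.1.4 and 16.2.4.1.5 each fit CDR-SB over EYO and compare the OLE Gant mITT population with all controls. Both state the same rule: "Because the baseline values of the OLE Gant mITT population were obtained before the treatment, these values will be counted into all controls". The exponential section repeats it when it defines the control arm: "data in this category include: baseline data of the OLE Gant mITT population and data of all controls". Neither section makes an exception by double-blind arm.

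The baseline in question is the OLE baseline. SAP 6.2.2: "OLE Baseline is defined as the latest non-missing DIAN-TU-001 measurement taken prior to OLE study drug administration". SAP 5.3 takes this population's data "for the OLE period, regardless of double-blind treatment, with controls" specified separately.

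Former gantenerumab participants are in this population by design. SAP 3.1: "Mutation positive subjects who were administered either gantenerumab/placebo to gantenerumab or solanezumab/placebo to solanezumab were allowed to participate in the OLE for gantenerumab". Protocol Appendix 3, section 3.1 agrees: "Any participant from either the gantenerumab or solanezumab blinded drug arms is eligible to enroll in the OLE period". SAP 16.2.4.1.2 names them as a group within it, since its Cox analysis is to be "repeated for the OLE Gant mITT population with 4 treatment groups (subjects on gantenerumab in the double-blind period" and three other groups.

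**The concern.** The control arm of these models is meant to show how the disease progresses over EYO without the drug under study. A participant from the double-blind gantenerumab arm reaches OLE baseline after a double-blind period that Protocol Appendix 3, section 1.9.2, puts at up to 4 to 7 years. That value predates OLE dosing but not gantenerumab.

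If the earlier treatment left some benefit, these values move the control curve toward the treated curve, and the estimated slowing is smaller than it would be with them left out. If it left none, nothing is biased from this source. What is at stake is how supportive estimates are read, not the trial's main conclusions.

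**Working it through.** No stated power, alpha or sample size figure depends on this rule, so there is no plan figure to reproduce. The check compares sections and then counts.

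**1. The stated reason against the definitions.** For double-blind placebo and solanezumab participants, OLE baseline precedes any gantenerumab and the reason holds. For double-blind gantenerumab participants, it precedes only the OLE course and the reason fails.

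**2. What the SAP does elsewhere.**
- Internal controls (SAP 5.4.2) are "the placebo data from the double-blind period among subjects who did not enter the open-label extension".
- The extended set (5.4.4) adds OLE baselines only for participants on double-blind placebo.
- The spline model (16.2.3.3) gives pooled controls a single slope on the ground that they were never treated.
- The whole-study PiB-PET model (16.1.4.3) treats OLE baseline as its fourth post-baseline visit.

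These sections govern other analyses, so the rule departs from the SAP's usual practice.

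**3. Which runs are touched.**

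| Run | Baseline of former gantenerumab participants | Affected |
|---|---|---|
| CDR-SB, both models, OLE Gant mITT (16.2.4.1.4, 16.2.4.1.5) | OLE | Yes |
| CDR-SB, both models, OLE Gant All Gant exposure mITT (same sections) | Double-blind | No |
| CSF Amyloid Beta1-42/40, logistic, OLE Gant mITT (16.2.4.4) | OLE | Yes |
| CSF Amyloid Beta1-42/40, logistic, All Gant exposure mITT (16.2.4.4) | Double-blind | No |
| CDR Global, logistic (16.2.4.2); OLE Cognitive Composite, both models (16.2.4.3) | Population not named for these models | Only if run on OLE Gant mITT |
| Primary PiB-PET (16.1.3) | No controls in the model | No |
| Primary CDR-SB and CDR Global (16.2.3.1, 16.2.3.2) | Rule not used | No |

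**4. How many values.** Inputs: 52 carriers on gantenerumab, 52 on solanezumab and 40 on placebo (Protocol 3.3), and an OLE goal of 60 to 90 (Protocol Appendix 3, 4.1.2).
- Total: 52 + 52 + 40 = 144. Gantenerumab share: 52/144 = 36.1%.
- Entry proportional to arm (assumption): 60 × 0.361 = 21.7 and 90 × 0.361 = 32.5, so about 22 to 33.
- Gantenerumab participants entering at half the others' rate (assumption): 26/(26 + 92) = 22.0%, giving 13 to 20. At twice the rate: 104/(104 + 92) = 53.1%, giving 32 to 48.
- Logical limits: the other two arms hold 52 + 40 = 92 people, enough to fill even 90 places, so the minimum is 0. The maximum is 52.

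The mITT also needs a post-baseline assessment, so actual counts may be lower.

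**5. Direction and rough size.** The bias cannot be computed: the documents give no carry-over estimate and no count of control records. A simplified simulation (random intercept only, assumed inputs, not the SAP model) gives an order of size. With 30% slowing in the OLE and 1 to 2 years of carry-over, the treatment coefficients were:
- −0.121 with these baselines kept and −0.129 with them left out: (0.129 − 0.121)/0.129 = 6.2% smaller.
- −0.137 and −0.150: (0.150 − 0.137)/0.150 = 8.7% smaller.

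With no carry-over the two runs agreed within simulation error.

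**The case against.** **Treatment here means OLE treatment.** The exponential model's treated arm holds only data after OLE baseline, so on that reading the sentence is literally true. This stands as a reading of the words. It does not rescue the use made of the values, which is to estimate the control arm's progression.

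**There may be nothing to carry over.** Protocol Appendix 3, section 1.4, reports no double-blind benefit on CDR-SB, and SAP 5.4.5 acknowledges a gap between the two treatment periods. The same protocol section calls the cognitive result inconclusive and reports biomarker effects. No double-blind result is given for CSF Amyloid Beta1-42/40, which SAP 16.2.1.1 expects to rise under effective drug. Carry-over can be neither assumed nor excluded.

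**The remedy is imperfect.** This has force. Subject-level random effects may absorb part of any shift. Carry-over also sits in these participants' post-baseline values, which stay in the treated arm, so dropping their baseline lets double-blind benefit count toward the estimate. Another simplified simulation (75 OLE participants, 36% with prior gantenerumab, 150 controls, 60 replicates, random intercept only) shows this. With no OLE effect, coefficients with baselines kept and left out were −0.036 and −0.034 at 1 year of carry-over, and −0.061 and −0.059 at 2 years (simulation SE about 0.003 to 0.004). With 30% slowing, the gap between keeping and leaving out was 0.006 with carry-over (−0.143 against −0.149) and 0.007 without (−0.112 against −0.119), so those runs do not isolate carry-over as the cause. The effect is small and its direction only modestly supported.

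**Stronger readings.** A reader might infer that the SAP contradicts its own control definitions; those sections cover other analyses, so it does not. A reader might also infer that it leaves open how OLE baselines after solanezumab are classed. It does not: the arm definition takes in all baseline data of the population, and those values precede any gantenerumab.

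**Conclusion.** The point holds as a minor correction to supportive analyses. The reason given for the rule is wrong for one identifiable group, so in the OLE Gant mITT runs the control curve is not purely untreated if any benefit carried over. About 22 to 33 values are involved, assuming the enrolment goal was met and entry followed the arm shares. That is a count of records, not of bias. Any pull toward no difference looks modest, and its size rests on assumed inputs.

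A reader might take this as undermining the OLE's efficacy findings. The documents do not support that: the main analyses do not use the rule, and for both CDR-SB and CSF Amyloid Beta1-42/40 the SAP already specifies a run in which these participants' baseline is the double-blind one.

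**What to change.** In SAP 16.2.4.1.4 and 16.2.4.1.5, count as controls only OLE baselines of participants with no double-blind gantenerumab. Amend the control-arm definition in 16.2.4.1.4 to match. Carry the rule into 16.2.4.2 to 16.2.4.4 wherever these models are run on the OLE Gant mITT, and name the population in 16.2.4.2 and 16.2.4.3.

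The cost is one sentence in each of two sections, one edited definition, and a flag from double-blind treatment data already held. One baseline value per former gantenerumab participant is lost from these runs. Carry-over in their later values then counts toward the gantenerumab effect, so the result should be described as total gantenerumab exposure against controls and read beside the OLE Gant All Gant exposure mITT run. The version 7 revision history shows that the interim had already ended the OLE, so the change must be recorded as made after the interim.

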16.2.4.1.5. Logistic Disease Progression Model

The logistic disease progression model with EYO as the continuous time variable as presented

Author: [REDACTED]

Version Number:

7

Version Date:

07Dec2023

Reference: CS WI BS005

Effective Date: 02Dec2019

below will be applied to the CDR-SB. The model will be used to estimate the slowing of disease progression in the OLE Gant mITT population compared to all controls. Because the baseline values of the OLE Gant mITT population were obtained before the treatment, these values will be counted into all controls for estimating the disease progression over EYO.

Briefly, the model can be described as:

$$Y_{ijk} = (\beta + \mu_i) + \frac{\gamma_1}{1 + e^{\left(\frac{-(EYO_{ij} + \delta_i) - \gamma_{3k}}{\gamma_{2k}} \right)}} + \varepsilon_{ijk},$$

where, y_{ijk} denotes the assessment for subject i at visit j in treatment arm $k = 1, 2$; treatment is a categorical variable with two categories: subjects the OLE Gant mITT population , and subjects in all controls; β is the mean of the healthy period (e.g. EYO ≤ -15) and is assumed to be the same for all groups; γ_1 is the mean decline from the healthy stage to the disease stage (e.g. EYO > 0) and is assumed to be the same for all groups; γ_{3k} is the EYO point where the disease progressed to the middle point between the healthy stage and the disease stage; γ_{2k} is the scale parameter indicating the spread of the disease progression curve; ε_{ijk} is the within-subject error and is assumed to follow a normal distribution $N(0, \sigma^2)$; μ_i and δ_i are the individual level random effects to account for the correlation among the repeated measures and use an unstructured covariance matrix. The main assumption of this model is that after accounting for the between subject difference though the random effects, the disease progression from EYO to EYO is the same for both cross-sectional data (from different subjects) and longitudinal data (repeated measurements of the same individual).

The treatment effect will be estimated by comparing the EYO points where the disease progressed to the middle point between the healthy period (β) and the disease period ($\beta + \gamma_1$). The null hypothesis is: $\gamma_{31} = \gamma_{32}$;

Author: [REDACTED]

Version Number:

7

Version Date:

07Dec2023

Template No.: CS_TP_BS016 Revision 6

Reference: CS_WI_BS005

Effective Date: 02Dec2019

and the alternative is: $\gamma_{31} \neq \gamma_{32}$.

The model will be used to estimate the slowing of disease progression in the OLE Gant mITT population compared to all controls.

If the model fails to converge, the random effect (δ_i) in EYO will be removed.

The model will also be used to compare OLE Gant mITT population and the OLE Gant All Gant exposure mITT populations, along with all controls.

Figures of model estimated mean over time by treatment arms or spaghetti plots of individual data over time/EYO by treatment arms will be presented as deemed necessary by Washington University team and may be included in CSR as needed.

The same analysis will also be conducted for the six subgroups defined in the first paragraph in [Section 16.2.4.1.1](#).

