6.5. STATISTICAL TESTS

The default significant level will be (5%); confidence intervals will be 95% and all tests will be two-sided, unless otherwise specified in the description of the analyses.

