16.2.4.3. Supplemental Analysis of the OLE Cognitive Composite

The supplemental analysis of the OLE Cognitive Composite will follow the logistic disease progression model in [Section 16.2.4.1.5](#) and the exponential disease progression model as described in [Section 16.2.4.1.4](#).

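### If the logistic progression model fails to converge, the SAP drops the random EYO shift and specifies no robust variance, so the 5% test of the midpoint shift can reject too often

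*SAP*

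**What the plan says.** The logistic model in SAP section 16.2.4.1.5 has two participant effects, which "are the individual level random effects to account for the correlation among the repeated measures": μ_i moves a person's whole curve up or down, and δ_i moves it along the EYO axis. Their covariance is unstructured. The SAP also states what the model relies on: "The main assumption of this model is that after accounting for the between subject difference though the random effects", progression along EYO is taken to be the same across people as within a person.

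"The treatment effect will be estimated by comparing the EYO points where the disease progressed to the middle point", that is, by testing γ31 = γ32. No level is set for this test, so section 6.5 applies: "The default significant level will be (5%); confidence intervals will be 95% and all tests will be two-sided". Treated participants' OLE baseline values are coded as control data: "these values will be counted into all controls for estimating the disease progression over EYO".

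For non-convergence there is one step: "If the model fails to converge, the random effect (δ_i) in EYO will be removed". No intermediate covariance structure, robust variance or bootstrap is mentioned.

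The section also applies the model to a second population, OLE Gant All Gant exposure, and to six amyloid-by-symptom subgroups. Sections 16.2.4.2 and 16.2.4.4 reuse it for CDR Global and CSF Aβ42/40. For the OLE Cognitive Composite, section 16.2.4.3 says that the supplemental analysis "will follow the logistic disease progression model".

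**The concern.** EYO is age minus an estimated age at onset. Under SAP Appendix 3 that estimate is the mean for the mutation wherever the mutation is listed. Actual onset scatters around the mean, and δ_i is the term that absorbs the scatter.

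The level effect μ_i cannot replace it. Take a curve with range 10 and scale 2.5 years, and three people whose EYO is at the midpoint: one on schedule, one 4 years behind and one 4 years ahead. With y = 10 / (1 + exp(-x/2.5)), where x is years past the midpoint, they change over three years as follows:

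- on schedule: 5.00 to 7.69, a rise of 2.69
- 4 years behind: 1.68 to 4.01, a rise of 2.33
- 4 years ahead: 8.32 to 9.43, a rise of 1.11

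A random intercept removes the difference in starting level but not the difference in change. Without δ_i, that remaining structure within a person is treated as independent error. The standard error of the midpoint contrast then comes out too small, and chance differences are read as slowing of disease more often than 5% of the time.

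**Working it through.** **Is δ_i likely to be material?** For mutation groups in SAP Table E, the SD of age at onset is SE × √n:

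| Mutation | SE | n | SD (years) |
|---|---|---|---|
| Ala431Glu | 0.4 | 97 | 3.9 |
| His163Arg | 0.5 | 63 | 4.0 |
| Val717Ile | 0.7 | 136 | 8.2 |
| Gly206Ala | 1.1 | 75 | 9.5 |
| Phe177Ser | 0.3 | 11 | 1.0 |
| Asn135Asp | 0.4 | 12 | 1.4 |
| Met139Ile | 0.5 | 12 | 1.7 |
| Gly217Arg | 0.6 | 18 | 2.5 |

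Timing therefore varies by several years in several large groups and by much less in some smaller ones.

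**Inputs.** From the documents: two-sided 5% (SAP 6.5); treated baseline coded as control (SAP 16.2.4.1.5); 60 to 90 enrolled and 5% annual dropout (protocol Appendix 3, section 4.1.2). The documents do not give the number of controls, the curve parameters, the SDs of μ_i, δ_i and the residual, or the EYO spread at OLE baseline. Assumed base case: 70 treated, 150 controls, baseline plus three annual visits, SD(δ) = 3 years, SD(μ) = 0.5, residual SD 0.7, range γ1 = 10, scale γ2 = 2.5 years.

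**The planned level first.** The only figure that the plan gives for this test is 5%. With both random effects kept and no treatment effect, the likelihood-ratio test rejected in 20 of 400 runs, or 5.0% (Monte Carlo error √(0.05 × 0.95 / 400) = 1.1 points). The model as planned holds its level.

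**The fallback.** Random intercept only, model-based Wald test at 1.96, no treatment effect, 2,000 runs per row (Monte Carlo error about 0.6 points at 9%). The last column uses a participant-level sandwich standard error.

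| Scenario | Rejects | With sandwich |
|---|---|---|
| Base case | 9.2% | 6.4% |
| SD(δ) = 2 / 4 / 5 / 7 years | 9.5 / 8.8 / 8.0 / 6.4% | 6.0 / 5.8 / 6.0 / 5.3% |
| 51 treated, 60 controls | 8.3% | 6.4% |
| 90 treated, 300 controls | 8.2% | 5.4% |
| Treated at later EYO (-5 to +15) | 9.5% | 7.2% |
| Residual SD 0.4 | 10.4% | 5.6% |
| γ1 = 16, γ2 = 2, SD(δ) = 4 | 12.6% | 6.5% |
| Eight visits per treated participant | 14.1% | 6.6% |
| γ1 = 12, γ2 = 1.5 | 14.6% | 6.0% |

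With SD(δ) near zero the rate was 4.8% (400 runs).

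**Where the excess comes from.** Bias was negligible. In the base case the estimated shift had an empirical SD of 0.239 years against a median model-based standard error of 0.206. The ratio is 0.206 / 0.239 = 0.862, so the nominal 1.96 acts as 1.96 × 0.862 = 1.69. The two-sided tail area beyond 1.69 is 9.1%, which matches the simulated 9.2%. For the steep curve, 0.183 / 0.253 = 0.723, giving 1.42 and 15.6%, close to the simulated 14.6%.

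**A second set of assumptions.** 65 treated, 150 controls, four annual values, range 18, scale 2.5, midpoint +6, residual SD 1, SD(δ) = 4 or 6 years. Runs with EYO between -10 and +10 or between -15 and +10 gave 8.2% to 10.6%, and EYO -5 to +15 gave 7.1% (450 to 500 runs each, Monte Carlo error about 1.3 points). A further set gave about 11-13%, about 15% with eight treated visits, and 6% with δ near zero. Another set gave 14.0% and 15.8% (400 runs each). Flatter or noisier variants gave less: 6.4% with range 10, 6.6% with residual SD 1.5 and SD(μ) = 1, and 5.0% with scale 4 years.

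**The case against.** The strongest case against is that the rule applies only when the full model fails to converge, whereas the simulations apply it to every dataset. If the usual cause of failure is a δ_i variance close to zero, removing the term does no harm. This stands in part: the failure rate is unknown, and the rates above are not conditional on failure. But Table E gives no reason to expect negligible scatter, and the six subgroups are small enough to fail for lack of data.

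A reader might infer a fixed error rate of 14-16%. The documents do not support that. They give none of the curve parameters, variance components or control numbers needed, and most runs fall below it. Rates of 12-17% arise readily if the rule that codes treated baselines as control is ignored, but the SAP does not ignore it. Nor is it safe to infer that the excess grows with the scatter in onset: in the 2,000-run scenarios it fell from 9.5% at 2 years to 6.4% at 7 years.

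A reader might also infer that the fallback abolishes the model's main assumption. The SAP rests that assumption on both random effects, and μ_i stays, so it is weakened rather than removed.

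One might wish to require that μ_i be dropped first for the CDR scales. That order was tested only with an assumed SD(μ) of 0.3, which builds in the answer, so it should not be required.

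Finally, little rests on this p-value. The primary CDR-SB analysis is a recurrent-event Cox model with robust variance (SAP 16.2.3.1), multiplicity is not controlled (7.4), the logistic model is optional and exploratory at the interim (section 17), and the SAP's version history says that the OLE ended early with an abbreviated report. All of this stands and sets the severity.

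**Conclusion.** The fallback is wrong as written, at minor severity. When onset timing truly varies, removing δ_i without a robust variance leaves the nominal 5% test of γ31 = γ32 anti-conservative: about 6-15% under no effect, typically 8-13%. The top of that range needs a steep curve or long follow-up. Long follow-up is relevant because the model is also applied to the population followed from double-blind baseline. There is little excess if the δ_i variance is near zero, and one run with a flat curve (scale 4 years) showed none.

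The size rests on assumed curve parameters, variance components, control numbers, EYO spread and follow-up. Only a CDR-SB-like scale was simulated. For CDR Global, the composite and CSF Aβ42/40 the mechanism carries over, but the size has not been estimated. The primary PiB-PET analysis is not touched.

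The gap is out of line with the SAP's own practice. Sections 16.1.3 and 16.1.4.3 set a sequence of covariance structures for the MMRM and require a sandwich estimator once a structured one is used.

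**What to change.** Replace the single fallback sentence in SAP section 16.2.4.1.5 with two steps:

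1. On non-convergence, set the μ_i-δ_i covariance to zero and refit with both effects.
2. If δ_i must still be removed, base the confidence interval and p-value on a participant-level sandwich variance or a bootstrap that resamples participants, and state in the output that the fallback was used.

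Apply the same rule wherever the model is reused: the six subgroups, CDR Global, the OLE Cognitive Composite and CSF Aβ42/40.

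In the 2,000-run scenarios the sandwich brought the rejection rate to about 5-7%. The bootstrap and the zero-covariance step were not simulated separately. Keeping δ_i where possible is worth the attempt: in the base case the SD of the estimated shift was 0.198 years with δ_i and 0.239 without, about 21% larger (0.239 / 0.198 = 1.21).

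The cost is a few lines of SAP text and code, and some computing time if the bootstrap is used. No data collection or other analysis changes.
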